1.1 Statement of ethical compliance

The study shall be conducted in compliance with the Clinical Trial Agreement (CTA), the Clinical Study Protocol (CSP), applicable Good Clinical Practice (GCP), and applicable regional or national regulations. The international standard for clinical study of medical devices for human subjects, ISO14155:2011 shall be followed. The International Conference on Harmonisation (ICH) guideline for GCP (E6) shall be followed as applicable for medical device. The study shall be conducted in accordance with the ethical principles that have their origin in the Declaration of Helsinki (Appendix 1).

1.2 Application to independent ethics committee and/or regulatory authorities

It is the responsibility of the Principal Investigator (PI) to obtain approval of the CSP/CSP amendment(s) from the independent ethics committee (IEC). The study shall not begin until the required favourable opinion from the IEC has been obtained. The PI shall file all correspondence with the IEC in the Investigator file and copies of IEC approvals shall be forwarded to the Sponsor. Any additional requirements imposed by the IEC or regulatory authorities (RA) shall be followed.

The collection, access to, processing, and transfer of protected health information or sensitive personal data shall be carried out in accordance with applicable rules and regulations.

2 Background Information

2.1 Indication and population description

As a medical device, Restylane Defyne is intended to augment the volume of facial tissues. In this study, it is intended for the correction of Chin Retrusion in subjects over the age of 18.

2.2 Investigational product description

Among the different materials used as raw materials in dermal fillers, sodium hyaluronate, also denoted hyaluronic acid when found in vivo and hereinafter referred to as HA, is the most frequently used¹. Hyaluronic acid is a naturally occurring polysaccharide found in all vertebrates and in some bacteria^{1,2}. The chemical structure is very simple with repeating disaccharide units of glucuronic acid and N-acetylglucosamine. As the chemical structure of HA is identical in all species and tissues, it is non-allergenic.

To minimize the risk for contamination, the HA used in the manufacture of Galderma's HA gels is of non-animal source, biosynthesized from *Streptococcus* species of bacteria. During manufacturing, cross-links are introduced between the HA chains to obtain a gel network and as a result the duration of the gel in the body is several months, as compared to only a few days for a solution of native HA. The HA gel is insoluble in water and organic solvents; however, the gel is highly hydrophilic and swells in water. Hyaluronic acid based fillers typically exhibit better biocompatibility and fewer adverse reactions than fillers based on

| | | |
|--|--|---------------------------|
|  GALDERMA | Title 43CH1627 Clinical Study Protocol | Doc id MA-34970 |
|--|--|---------------------------|

2018-01-15 10:39

Effective date:

Effective

Version: 3.0

other materials. The gel, when injected, acts by increasing the tissue volume, thereby improving tissue structure and support. The gel is gradually degraded over time and eventually the correction made will subside.

Restylane Defyne is a sterile, biodegradable, transparent gel of non-animal cross-linked HA containing a concentration of 20 mg HA per mL in a physiological buffer system. Lidocaine hydrochloride (3 mg/mL) is added to the formulation to diminish the pain resulting from the injection during the treatment. When the gel is injected and the tissue expands some pain can be experienced and it is therefore desirable to have a local anesthetic effect at the site of injection.

Restylane Defyne has been regulatory cleared under the brand name Emervel Deep lidocaine in more than 50 countries from most continents of the world including the US, Europe, Canada, Latin America, Australia, and Asia. The intended use, in the region of origin (Europe), is facial tissue augmentation for the correction of severe wrinkles or to redefine the shape of the face (cheeks, tear troughs, or lips). The regulatory cleared intended use differs between different countries. Depending on the area to be treated and the tissue support, the product should be injected in the mid to deep dermis, submucosal layer of the lips, subcutis, or supraperiostic zone.

The gel in Restylane Defyne is, produced using the Optimal Balance Technology (OBT).

2.3 Reference product description

Not applicable as no dermal filler intended for Chin retrusion correction is available in China at the time of this protocol.

2.4 Previous experience

2.4.1 Non-Clinical Documentation

Products manufactured using the OBT process have been tested and meet all biocompatibility requirements specified in the international standard ISO 10993:1 (Biological Evaluation of Medical Devices; i.e., having no toxic or injurious effects on the human body)^{3,4}; it is neither cytotoxic nor genotoxic, and it does not give rise to acute toxicity, pyrogenicity, skin irritation, or delayed sensitization.

In in vivo animal studies, the OBT products demonstrated good filler longevity, similar or superior to comparator products, and all products were well tolerated with minimal microscopic inflammation scores secondary to limited tissue disturbance.

2.4.2 Clinical Documentation

The safety of and performance of Emervel Deep and Restylane Defyne have been evaluated in two randomized controlled studies focusing on nasolabial folds, in one open label study with full-face treatment with the Emervel range of products and in a large observational study.

Restylane Defyne has been evaluated in a 1-year, randomized, evaluator-blinded, active controlled, multi-center, split-face comparison US study of the two HA fillers Restylane Defyne and Juvéderm Ultra Plus with the objective to compare efficacy and safety¹². One hundred sixty-two (162) subjects with moderate to severe NLFs were treated with Restylane

| | | |
|--|---|----------------------------|
|  | 
Title 43CH1627 Clinical Study Protocol
 | 
Doc id MA-34970
 |
|--|---|----------------------------|

Defyne in one NLF and Juvéderm Ultra Plus in the other. Non-inferiority of Restylane Defyne compared with Juvéderm Ultra Plus was demonstrated. Restylane Defyne showed a favorable safety profile in subjects with moderate to severe wrinkles and folds, and was comparable to Juvéderm Ultra Plus.

Another randomized, evaluator-blinded study in Europe comparing Emervel Deep (identical to Restylane Defyne but without lidocaine) with Restylane Perlane in 86 subjects, demonstrated similar safety between the dermal fillers and a superior, albeit of limited clinical relevance, efficacy of Emervel Deep after NLF correction ^{13, 14}.

The performance and safety of the use of Emervel Deep were evaluated for several other indications in an open-label full-face treatment study ^{6, 15, 16}. These indications included marionette lines (n=92) and tear troughs (n=15). The performance was demonstrated in terms of wrinkle severity improvement and/or aesthetic improvement. In addition, high patient satisfaction was recorded. The improvement was demonstrated to last for up to 6 months for these indications.

In addition, in a large observational study performed in France ⁸, 1822 patients were treated with one or more of the Restylane Emervel Collection of products. As it was a non-interventional study product choice and injection volumes were at the discretion of the 58 participating physicians. Emervel Deep was used for several treatment areas including nasolabial folds, marionette lines, tear trough, lip corners, cheek volume, supramental crease, and vertical lip lines. This study investigated mean volumes injected, injection techniques used and tolerance. Performance was not evaluated.

Another Emervel filler products, Restylane Volyme, was evaluated in an 18-month open study¹⁷ in 60 subjects with at least Grade 2 on the 4-point volume loss scale (VLS) for full face and at least 2 indications affected among chin, temporal areas, jawline, cheeks, cheekbones, and NLF. Performance was assessed by VLS, Lemperle rating scale (LRS), investigator GAIS, and 3-dimensional (3D) imaging. At 18 months, at least a 1-grade improvement in VLS was observed for full face (68.3% of subjects), chin (77.8%), temporal areas (73.7%), cheeks (66.6%), cheekbones (58.6%), jawline (43.1%), and NLF (71.4%; LRS). For all indications, more than 60% of the volume gained at 3 weeks was sustained at 18 months based on 3D digital imaging. At 18 months, 95.0% of subjects had improved full-face GAIS and all subjects were satisfied with their aesthetic outcome. One subject (1.6%) had treatment-related adverse events.

Post market surveillance data for Restylane Defyne also support that the AE profile is acceptable.

2.5 Study rationale and Justification for design

Chin profile is an important component of the full facial appearance. In Asian people, chin retrusion is very common and many people would like to correct it because chin retrusion may be considered as unattractive. In clinical practice, surgical techniques, such as osteotomy or insertion of implants are commonly used for chin retrusion correction. More recently, HA injection for Chin augmentation has been reported in Chinese people^{18, 19}. However, no HA filler intended for Chin Retrusion correction has been approved in China.

Although no published data for Restylane Defyne in Chin retrusion treatment, satisfied outcome was showed in anecdotal report. Also, pre-clinical testing/previous clinical

| | | |
|--|--|---------------------------|
|  | Title 43CH1627 Clinical Study Protocol | Doc id MA-34970 |
|--|--|---------------------------|

Effective date: 2018-01-15 10:39

Effective

Version: 3.0

experience as described in Section 2.4, have demonstrated acceptable performance and safety for Restylane Defyne when used for facial tissue augmentation. Therefore, the Sponsor consider it justified to conduct a study to investigate Restylane Defyne for the treatment of Chin Retrusion. The study will be used as clinical documentation for registration of the product in China. No treatment control is chosen as no HA filler intended for Chin Retrusion correction is available in China at the time of this protocol.

2.6 Risk and benefits

By January 2017, Restylane Defyne has been regulatory cleared in 50 countries/regions, including US, EU, Canada, Australia, Hong Kong, Korea, India, etc. It is considered safe and effective for facial tissue augmentation.

As all other injectable medical devices, Restylane Defyne has the potential to cause complications. Most events are related to the injected volume and injection technique, though some could be associated with properties or constitutes of the gel itself. After the injection of Restylane Defyne, some common injection-related reactions might occur. These reactions include bruising, erythema, swelling, pain, tenderness, or itching at the implant site. Typically, resolution is spontaneous within one week after injection into the skin. The intensity and duration of these events are usually considered tolerable by a majority of subjects. The study product will be administered in accordance with the instructions in section 6.6.

The primary potential benefit of the study is a perceived improvement in the treated areas. However, there is a risk that the subject will not gain the full aesthetic correction of Chin Retrusion. There is also a risk for development of palpable lumps or displacement of the injected gel. Inflammation or infection have been reported in a few cases after HA filler treatment. There may be risk of damaging body structures such as nerves or blood vessels connected to the injection site, however these risks are minor. Following facial aesthetic treatments isolated rare cases have been reported regarding ischemic events affecting the eye leading to visual loss, and the brain resulting in cerebral infarction. Detailed information on reported AEs relevant for Restylane Defyne is provided in the IB.

Lidocaine can in rare cases give allergic reactions, and therefore subjects with known allergy or hypersensitivity to local anaesthetics should not be included in the study.

The frequency of post market AE reporting is based on the number of units sold. The reporting frequency of AEs assessed as related to Restylane Defyne are ranging from seldom (approximately 1/1 000 – 1/10 000 events per sold unit) to rare/ isolated cases (i.e., <1/100 000 events per sold unit).

The risks related to HA filler injections for facial tissue augmentation have been judged to be low, based on nonclinical data (Section 2.4.1), experience from clinical studies (Section 2.4.2) and post-marketing data. Given the anticipated low level of transient and acceptable AEs in connection with the injection, the risk-benefit assessment of the use of Restylane Defyne for treatment of Chin retrusion appears to offer a clinical benefit at reasonable risk.

Only study investigators qualified by education and experience, and who are skilled in the use of dermal fillers from their clinical practice and involvement in clinical research, will be chosen in order to assure proper device implantation and management of study risk.

| | | |
|--|---|--|
|  GALDERMA | <small>Title</small> 43CH1627 Clinical Study Protocol | <small>Doc id</small> MA-34970 |
|--|---|--|

Effective date: 2018-01-15 10:39

Effective

Version: 3.0

3 Objective and Endpoints

3.1 Objective of the study

- To evaluate the effectiveness and safety of Restylane Defyne versus a no-treatment control in the treatment of Chin Retrusion.

3.2 Endpoints of the study

3.2.1 Primary effectiveness endpoint:

- Percentage of responders, defined by at least 1 point improvement from baseline on the Galderma Chin Retrusion Scale (GCRS), as measured by the Blinded Evaluator at 6 months (after last treatment in Treatment Group, and after randomization in Control Group).

3.2.2 Secondary effectiveness endpoints:

- Percentage of responders, defined by at least 1 point improvement from baseline on the GCRS, as measured by the Blinded Evaluator at 3, 9 and 12 months after last treatment in Treatment Group, and at 3 months after randomization, as well as 3, 6, 9 and 12 months after the last treatment in Control Group.
- Percentage of responders, defined by at least 1 point improvement from baseline on the GCRS, as measured by the Treating Investigator at each follow up visit.

CCI

3.2.3 Safety endpoints:

- Incidence, intensity, duration, and onset of adverse events (AEs) collected throughout the study.

CCI

4 Design of the Study

4.1 General Outline

This is a randomized, evaluator-blinded, no-treatment controlled study in subjects with Chin Retrusion.

Subjects will be screened for eligibility within 21 days prior to Baseline. Eligible subjects will be randomized either to the Treatment Group or the Control Group in a 3:1 ratio.

| | | |
|--|--|---------------------------|
|  GALDERMA | Title 43CH1627 Clinical Study Protocol | Doc id MA-34970 |
|--|--|---------------------------|

Effective date: 2018-01-15 10:39

Effective

Version: 3.0

Treatment

Each subject assigned to the Treatment Group will receive an initial treatment on Day 1. A touch-up treatment may be performed 4 weeks after the initial treatment if optimal chin augmentation has not been obtained. Optimal chin augmentation is defined as the best possible aesthetic result that can be obtained for an individual study participant, as agreed upon by the Treating Investigator and subject. At least one (≥ 1) grade improvement from baseline on the GCRS should be the treatment target.

Subjects assigned to the Control Group will not receive treatment at baseline but will return for routine follow-up. At month 6 visit after randomization, subjects in Control Group will be offered a treatment and, at the following visit, an optional touch-up treatment.

Evaluation of effectiveness

Chin Retrusion will be assessed using a separate Four-Point GCRS with photo guides by the Treating Investigator at each visit; and by the Blinded Evaluator at screening, baseline, 3, 6, 9 and 12 months after last treatment in Treatment Group, and at screening, baseline, 3 and 6 months after randomization, as well as 3, 6, 9 and 12 months after last treatment in Control Group.

CCI

Evaluation of safety

Information regarding AEs will be collected continuously during the study. CCI

CCI

| | | |
|--|--|---------------------------|
|  GALDERMA | Title 43CH1627 Clinical Study Protocol | Doc id MA-34970 |
|--|--|---------------------------|

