4.6 Concomitant Medication, Treatment, and Procedure

Except as noted below, concomitant medications or other treatments or procedures may be utilized when the PI or his/her authorized designee considers it medically necessary.

| | | |
|--|--|---------------------------|
|  | Title 43CH1627 Clinical Study Protocol | Doc id MA-34970 |
|--|--|---------------------------|

Effective date: 2018-01-15 10:39

Information regarding any use of concomitant medications, including over-the-counter medications administered during the study is to be recorded in the eCRF. The generic name or the trade name of all concomitant medication or a description of the procedure and the reason for its use shall be documented in the eCRF.

The following medications, treatments, and procedures are restricted or prohibited during the study:

- Thrombolytics, anticoagulants or inhibitors of platelet aggregation (e.g. aspirin or other non-steroidal anti-inflammatory drugs [NSAIDs]), Omega-3, or Vitamin E should not be used within two weeks before treatment to avoid increased bruising or bleeding at injection sites.
- Lidocaine should be used with caution in patients receiving other local anesthetics or agents structurally related to amide-type local anesthetics e.g., certain antiarrhythmics, since the systemic toxic effects can be additive.
- Concomitant treatment with chemotherapy, immunosuppressive agents, immunomodulatory therapy (e.g., monoclonal antibodies) is prohibited.
- Long term concomitant treatment with systemic or topical (facial) corticosteroids is prohibited (inhaled corticoids are allowed). Corticosteroids should be used with caution and should be adjudged as necessary by the Investigator.
- Use of systemic or topical (facial) retinoic acid is prohibited.
- Facial tissue augmenting therapy, contouring or revitalization treatment with fillers, lifting threads, permanent implant, needling, mesotherapy, radiofrequency, ultrasound, cryotherapy, fat-injection, neurotoxin, laser or light treatment, chemical peeling or dermabrasion below the level of the horizontal line from subnasale are prohibited.
- Planned surgery including aesthetic facial surgical therapy or facial liposuction, sinus surgery, dental root surgery or dental work, piercing or tattoo in the area to be treated is prohibited.
- Participation in any other clinical study is prohibited

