**CCI**

| | | | | | | |
|---------------------|---|---|---|---|---|---|
| Device deficiencies | | X | X | | | |
| Assessment of AE | X | X | X | X | X | X |
| Study termination | | | | | | X |

- a) Screening visit and baseline visit can be combined to one visit if feasible.
- b) This visit is only for subjects who receive touch-up (If no touch-up performed, subjects will conduct the 4w after last treatment visit).
- c) Prior to randomization.
- d) Prior to treatment.
- e) Only performed at 6M.
- f) Only performed at early termination if termination occurs before 6 months visit after last treatment.
- g) Only performed at CCI 6M.
- h) Serum pregnancy test (S-HCG).
- i) Urine pregnancy test (U-HCG).
- j) Only performed if the screening S-HCG was done \geq 2 weeks before baseline.

Table 2. Schedule of Events for Control Group

| Activity | Control Group | | | | | | | | | |
|---------------------------------------|------------------------|-----------------------|-----------------------------------|------------------------------------|-----------------------------------|----------------------------------|------------------------------------|---|--------------------------------------|--|
| | Screening ^a | Baseline ^a | Follow-up | Follow-up | Follow-up /Treatment | Optional Touch-up ^b | Follow-up | Follow-up | Final visit / Early termination | |
| | D-21 to 1 | D1 | 4W(\pm 3d) after randomization | 3M (\pm 1w) after randomization | 6M(\pm 1w) after randomization | 4W(\pm 3d) after 6M treatment | 4W(\pm 3d) after last treatment | 3M (\pm 1w), 6M(\pm 1w) and 9M (\pm 2w) after last treatment | 12M (\pm 2w) after last treatment | |
| Informed consent | X | | | | | | | | | |
| Demography | X | | | | | | | | | |
| Medical history & concurrent diseases | X | X | | | | | | | | |
| Concomitant medication/procedures | X | X | X | X | X | X | X | X | X | |
| Vital signs | | X ^c | | | X ^d | | | | | |
| Laboratory tests | X | | | | X ^d | | | X ^e | X ^f | |

| | | | | | | | | | |
|----------------------------------|----------------|--------------------|---|---|------------------|------------------|---|---|----------------|
| ECG | X | | | | | | | | |
| Pregnancy test | X ^g | X ^{c,h,i} | | | X ^{d,h} | X ^{d,h} | | | X ^h |
| Inclusion and Exclusion criteria | X | X | | | | | | | |
| Randomization | | X | | | | | | | |
| Treatment | | | | | X | X | | | |
| GCRS(Blinded Evaluator) | X | X | | X | X ^d | | | X | X |

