| GCRS (Treating Investigator) | X | X | X | X | X ^d | X ^d | X | X | X |
| Photography | | X | X | X | X ^d | X ^d | X | X | X |
| CCI | | | | | | | | | |
| Device deficiencies | | | | | X | X | | | |
| Assessment of AE | X | X | X | X | X | X | X | X | X |
| Study termination | | | | | | | | | X |

- a) Screening visit and baseline visit can be combined to one visit if feasible.
- b) This visit is only for subjects who receive touch-up (if no touch-up performed, subjects will conduct the 4w after last treatment visit).
- c) Prior to randomization.
- d) Prior to treatment.
- e) Only performed at 6M after last treatment
- f) Only performed at early termination if termination occurs before 6 months visit after last treatment.
- g) Serum pregnancy test (S-HCG).
- h) Urine pregnancy test (U-HCG).
- i) Only performed if the screening S-HCG was done ≥ 2 weeks before baseline.
- j) Only performed at **CCI** 6M after last treatment.

| | | |
|--|--|-----------------------------------|
|  | 
Title 43CH1627 Clinical Study Protocol
 | 
Doc id MA-34970
 |
|--|--|-----------------------------------|

Effective date: 2018-01-15 10:39

Effective

Version: 3.0

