4.8.2.2 Baseline (D1)

- Medical history/concurrent diseases
- Vital signs (pulse rate, blood pressure, respiratory rate, body temperature)
- Inclusion and exclusion criteria

| | | |
|--|--|-----------------------------------|
|  | 
Title 43CH1627 Clinical Study Protocol
 | 
Doc id MA-34970
 |
|--|--|-----------------------------------|

Effective date: 2018-01-15 10:39

Effective

Version: 3.0

- U-HCG for childbearing potential women (Only performed if the screening S-HCG was done ≥ 2 weeks before baseline)
- Photography
- Randomization
- GCRS (by Blinded Evaluator and Treating Investigator)
- Concomitant medications /procedures
- AE since last visit

4.8.2.3 4W ($\pm 3d$) Follow-up after randomization

- Photography
- GCRS (by Treating Investigator)

CCI [REDACTED]

- Concomitant medications /procedures
- AE since last visit

4.8.2.4 3M ($\pm 1w$) Follow-up after randomization

- Photography
- GCRS (by Blinded Evaluator and Treating Investigator)

CCI [REDACTED]

- Concomitant medications /procedures
- AE since last visit

4.8.2.5 6M ($\pm 1w$) Follow-up after randomization / treatment

- Vital signs (pulse rate, blood pressure, respiratory rate, body temperature)
- laboratory tests (haematology and serum chemistry)
- U-HCG for childbearing potential women (before injection)
- GCRS (by Blinded Evaluator and Treating Investigator)
- Photography (before injection)

CCI [REDACTED]

- Treatment

CCI [REDACTED]

- Concomitant medications /procedures
- Device deficiencies
- AE since last visit

4.8.2.6 Optional Touch-up 4W ($\pm 3d$) after 6M treatment (only for subjects who received touch-up)

- Photography (before injection)
- GCRS (by Treating Investigator)

CCI [REDACTED]

- U-HCG for childbearing potential women (before injection)
- Treatment

CCI [REDACTED]

| | | |
|--|--|---------------------------|
|  GALDERMA | Title 43CH1627 Clinical Study Protocol | Doc id MA-34970 |
|--|--|---------------------------|

- Concomitant medications /procedures
- Device deficiencies
- AE since last visit

4.8.2.7 4W ($\pm 3d$) Follow-up after last treatment

- Photography
- GCRS (by Treating Investigator)

CCI

- Concomitant medications /procedures
- AE since last visit

4.8.2.8 3M ($\pm 1w$), 6M ($\pm 1w$) and 9M ($\pm 2w$) Follow-up after last treatment

- Photography
- GCRS (by Blinded Evaluator and Treating Investigator)

CCI

[figure not shown]

- Concomitant medications /procedures
- Laboratory tests (Only performed at 6M)
- AE since last visit

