14. Subjects presenting with porphyria.
15. Tendency to form keloids, hypertrophic scars, or any other healing disorder.
16. History of bleeding disorders or treatment with thrombolytics, anticoagulants or inhibitors of platelet aggregation (e.g. aspirin or other non-steroid anti-inflammatory drugs (NSAIDs), Omega-3, or vitamin E within 2 weeks before treatment.
17. Treatment with chemotherapy, immunosuppressive agents, immunomodulatory therapy (e.g. monoclonal antibodies), systemic corticosteroids within 3 months before treatment (inhaled corticoids are allowed).
18. Treatment with topical (facial below the level of the horizontal line from subnasale) retinoids or corticosteroids within 1 month, or systemic retinoids within 6 months before treatment.
19. Any medical condition that in the opinion of the Investigator would make the subject unsuitable for inclusion.
20. Other condition preventing the subject from entering the study in the Investigator's opinion, e.g. subjects not likely to avoid other facial cosmetic treatments, subjects anticipated to be unreliable, unavailable or incapable of understanding the study assessments or having unrealistic expectations of the treatment result.

| | | |
|--|--|---------------------------|
|  GALDERMA | Title 43CH1627 Clinical Study Protocol | Doc id MA-34970 |
|--|--|---------------------------|

2018-01-15 10:39

Effective date:

Effective

Version: 3.0

21. Women who are pregnant or breast feeding, or Woman of childbearing potential who are not practicing adequate contraception or planning to become pregnant during the study period.
22. Subjects planning to accept any other facial plastic surgical or cosmetic procedures below the level of the horizontal line from subnasale during the study (e.g., laser or chemical resurfacing, needling, facelift, radiofrequency etc.).
23. Study site personnel, close relatives of the study site personnel (e.g. parents, children, siblings, or spouse), employees, or close relatives of employees at the Sponsor Company.
24. Participation in any other clinical study within 30 days before treatment.

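### Control subjects get their first injection about six months after their last exclusion check, and no rule says when to delay or withhold it

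*Protocol*

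**What the plan says.** **First Control injection.** Protocol Section 4.1 (and the synopsis): "At month 6 visit after randomization, subjects in Control Group will be offered a treatment and, at the following visit, an optional touch-up treatment". Section 4.8.2.5 gives the visit as Month 6 ± 1 week, under the title "Follow-up after randomization / treatment".

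**Eligibility check.** In the Control Group schedule (Section 4.7, Table 2) the row reads "Inclusion and Exclusion criteria | X | X". The two marks are at screening and baseline, and the Month 6 cell is blank. The list in 4.8.2.5 has no such item either. In the Treatment Group schedule the second mark is in the column of the initial treatment.

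**Exclusions timed from treatment (Section 5.3).** No. 17 includes "systemic corticosteroids within 3 months before treatment (inhaled corticoids are allowed"). No. 18 bars topical corticosteroids on the lower face in the month before treatment. No. 12 bars recent dental, oral or sinus surgery, with a look-back of 12 months in Section 5.3 and 6 months in the synopsis. No. 9 bars disease or lesions at or near the site, and nos. 1 to 3 concern allergy.

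**On-study rules (Section 4.6).** "Long term concomitant treatment with systemic or topical (facial) corticosteroids is prohibited"; the same bullet asks for caution with corticosteroids and leaves their necessity to the Investigator. "Planned surgery including aesthetic facial surgical therapy or facial liposuction, sinus surgery, dental root surgery or dental work" is also prohibited. Use of something prohibited is documented as a deviation, and the subject continues scheduled follow-up.

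**What is repeated before the Month 6 injection.** Vital signs, laboratory tests, a urine pregnancy test and the GCRS are marked as done before treatment.

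**The concern.** Several exclusions are defined by time before treatment. For the Treatment Group, treatment is on Day 1 and the check is made that day. For the Control Group, treatment is six months later and the check is not repeated, so a safeguard built around the injection is never formally applied to these subjects' first exposure.

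Followed as written, the plan lets a Control subject be injected in circumstances that would exclude a Treatment subject on Day 1. An example is a short oral steroid course in month 5, which breaks no stated prohibition. Section 2.6 names inflammation, infection and lidocaine allergy among the risks. What is at stake is protection of subjects at first exposure, not the comparison between groups.

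**Working it through.** The plan gives no figure on this point, and the question is mainly one of setting sections side by side. The arithmetic concerns timing and numbers exposed.

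**1. Age of the check at first injection.** Taking a month as 365.25/12 days, six months = 6 × 365.25/12 = 182.6, about 183 days. With the ± 7 day window (Table 2, Control): 183 − 7 = 176 to 183 + 7 = 190 days. Treatment Group: 0 days.

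**2. How much of each look-back falls after the Day 1 check.** Share = min(1, gap / look-back).
- Topical facial steroids, 1 month (about 30 days): 176/30 exceeds 1, so 100%.
- Systemic steroids, 3 months (about 91 days): 176/91 exceeds 1, so 100%.
- Dental, oral or sinus surgery, 6 months (synopsis): 176/183 = 96% up to 100%.
- The same, 12 months (Section 5.3): 176/365 = 48% to 190/365 = 52%.

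The Day 1 check therefore sees none of either steroid window, and at most about half of the surgery window. The conclusion does not depend on which surgery look-back is right.

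**3. Which exclusions are carried forward by other means.**

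| Exclusion | On-study cover | Tied to delaying or withholding the injection? |
|---|---|---|
| Platelet inhibitors, anticoagulants, NSAIDs (16) | 4.6, two weeks before treatment | Timing rule stated |
| Immunosuppressants; fillers, neurotoxin and similar procedures (17, 6–8) | 4.6 prohibition, deviation documented | No, but prohibited throughout |
| Pregnancy (21) | Urine test before the injection (4.8.2.5, 8.2) | No action on the injection stated; 8.4.7 covers reporting and follow-up |
| Short-course steroids (17, 18) | 4.6: caution, Investigator judgement on need | No |
| Unplanned dental, oral or sinus surgery (12) | None; 4.6 addresses planned surgery | No |
| New site disease or new allergy (9, 1–3) | May be reported as an AE (8.4.1, 8.4.3) | No |

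Section 5.5 allows withdrawal from the study, which is not a rule for postponing an injection. Section 6.6 has no postponement rule.

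**4. Number exposed.** Control Group 37; after 15% drop-out 37 × 0.85 = 31.45, about 31. If every subject is injected, Control subjects are 37/148 = 25% of those treated.

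**5. Primary endpoint.** The Control GCRS at Month 6 is rated before treatment (Table 2), so neither the gap nor its repair touches it.

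**The case against.** **Entry criteria govern entry.** Section 5.3 excludes from enrolment, Section 4.6 is the on-study rule set for both groups, and Treatment Group touch-ups are also given without a repeat check. This stands as a coherent reading, and for that reason the point is a missing safeguard, not a contradiction. A touch-up, however, follows a checked or recent injection by four weeks; the Control Group's Month 6 injection is a first exposure.

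**Discretion already covers it.** Treatment is only offered, Section 2.6 requires skilled injectors, Section 5.5 lets the Investigator discontinue a subject, and Section 4.6 leaves short steroid courses to the Investigator. All true, and a careful Investigator would probably act. But the steroid sentence concerns whether the drug is needed, not whether a later injection should go ahead. The same discretion exists on Day 1, where the protocol still requires a formal check.

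**Unseen material.** The Investigator's Brochure and instructions for use are not available here, and 4.8.2.5 has redacted items. Product-level contraindications may exist there. The eligibility row of the Control schedule is nevertheless visible and blank at Month 6.

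**Stronger readings a reader might infer.**
- That medication and AE questions may be asked after the injection, because those rows lack a before-treatment mark and come after treatment in 4.8.2.5. The Treatment Group's Day 1 column and list have the same layout, so this shows nothing specific to Control.
- That retinoids are a further gap, because 4.6 says "Use of systemic or topical (facial) retinoic acid is prohibited" while exclusion 18 speaks of retinoids. That is a difference of wording, not a demonstrated safety gap.
- That the pregnancy test is missing. It is fixed before the injection; only the action on a positive result is unstated.

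**Conclusion.** The point holds as a minor safety improvement. At their first injection, up to 37 Control subjects (about 31 if the planned drop-out occurs by Month 6) rely on an exclusion check that is 176 to 190 days old. Short-course steroids, unplanned dental, oral or sinus surgery, and new site disease or allergy have no stated consequence for that injection beyond Investigator discretion.

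The documents give no rate at which subjects would acquire such a condition and no risk attached to it, so no expected harm can be calculated. Because the SAP pools Control events after the Month 6 injection into the Restylane Defyne columns (Tables A 41 and A 43 to A 47), a reader might infer that the safety results are distorted. Nothing in the documents supports a size or direction for that. No bias and no effect on the primary endpoint is claimed.

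The conclusion assumes that no redacted item at the Month 6 visit, and no product document outside the protocol, already supplies a rule to delay or withhold.

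**What to change.** In Table 2 (Control Group) and Section 4.8.2.5, add one check of the treatment-relevant exclusion criteria at the Month 6 visit, marked as done before treatment and made by the Treating Investigator. The GCRS entry grade need not be rechecked. The sponsor's clinicians should name the criteria that apply.

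Make the offer in Section 4.1 and the synopsis conditional on the check. State that the injection is delayed or withheld if a criterion is met or the pregnancy test is positive, and that the subject stays in follow-up. After a delay, visits already run from the actual last treatment. Timing for a subject who is never injected should be stated; that question exists anyway because treatment is optional.

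**Cost.** A protocol amendment with ethics committee approval (Section 12.3) at approximately 5 sites, and an eCRF page copied from baseline. No new procedure is needed.

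**Lost information.** Slightly fewer Control subjects give descriptive post-treatment data. As illustration, with assumed responder rates r and the normal approximation 1.96 × √(r(1 − r)/n), the 95% half-widths in percentage points are:

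| Assumed r | n = 31 | n = 30 | n = 28 |
|---|---|---|---|
| 0.6 | 17.2 | 17.5 | 18.1 |
| 0.8 | 14.1 | 14.3 | 14.8 |
| 0.9 | 10.6 | 10.7 | 11.1 |

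Withholding the injection from three of 31 subjects would widen the interval by less than one point on each side.
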